7.4.2.2 Final Analysis of Primary Effectiveness Endpoint

If trial success is not declared at the early success interim, the final analysis for the primary effectiveness endpoint will use a beta-binomial model with a non-informative uniform prior Beta (1,1) based on complete 12-month follow-up data. At the time of the final analysis, the primary effectiveness endpoint will be considered as success if:

$$\Pr(p_E > 0.50|x, n) > 0.9775$$

where p_E is the 12-month effectiveness success rate. If the posterior probability of the effectiveness rate being greater than 50% is greater than 0.9775 then the study will be considered to have demonstrated effectiveness of the device.

To investigate the robustness of the analysis result, the following sensitivity analyses will be performed in the mITT and PP analysis sets unless otherwise noted at the time of the final effectiveness analysis:

- **Sensitivity to Analysis Set**

The primary effectiveness endpoint will be analyzed in the mITT analysis set as a sensitivity analysis.

- **Snap-Shot Binomial Analysis**

Number and percentage of subjects free from primary effectiveness failure will be presented along with one-sided 97.75% exact binomial lower confidence bounds. Subjects with missing outcomes will be excluded from this analysis. Missing outcomes of primary effectiveness endpoints is defined in Section 7.4.3.

- **Kaplan-Meier Analysis**

Kaplan-Meier estimates and plots will be used to characterize the time to first primary effectiveness event, including acute procedural failure and documented symptomatic/asymptomatic AF, AT, or AFL recurrence following the initial ablation procedure. This will provide a non-parametric estimate of the primary effectiveness endpoint. The Kaplan-Meier analysis will account for all follow-up time for all subjects in the analysis set. Subjects with incomplete follow-up who remain failure free will be censored at the time of last observation. The probability of freedom from primary effectiveness failure at each monthly timepoint post blanking will be presented along with the one-sided 97.75% lower confidence bound using Greenwood's variance.

- **Best-case Scenario**

The point estimate for freedom from primary effectiveness failure will be estimated by treating subjects with missing primary effectiveness outcomes as free from primary effectiveness events.

- **Worst-case Scenario**

The point estimate for freedom from primary effectiveness failure will be estimated by treating subjects with missing primary effectiveness outcomes as failures.

- **Tipping Point Analysis**

Tipping point analysis will be performed for the primary effectiveness endpoint to assess the impact of missing outcomes on the effectiveness conclusion. The posterior distribution will be updated each time treating a subject with a missing outcome as failure to evaluate whether a tipping point is identified.

If early success is achieved, the primary effectiveness endpoints and associated sensitivity analyses based on full 12-month follow-up data will be summarized descriptively – raw rates based on completers, and Kaplan-Meier estimates based on full follow-up will be presented.

7.4.3 Handling of Missing Data

Missing data will be queried for reasons and handled on an individual basis.

- **Sample Size Selection Interim Analysis:** For the sample size selection interim analyses, subjects with incomplete follow-up data for the effectiveness endpoint will be censored at the time of their last follow-up visit, and only their observed partial follow-up time will contribute to the estimation of model parameters and compute the predictive probability of the effectiveness success.
- **Early Success Primary Safety Endpoint:** For the early success interim analysis of the safety endpoints, if a subject's 3-month follow-up is not complete but a PAE has occurred prior to 3-month follow-up, the subject will be considered as having an event. If a subject exits the study without completing their 3-month follow-up visit and the subject has not had a PAE, that subject will be excluded from the early success safety analysis.
- **Early Success Primary Effectiveness Endpoint:** For the early success interim analysis of the effectiveness endpoints, subjects with incomplete follow-up data will be censored at the time of their last follow-up visit (if event-free). For these subjects, only their observed partial follow-up time will contribute to the estimation of model parameters. Subjects who refuse the remote arrhythmia/holter monitoring device will be excluded from the early success effectiveness analysis.

- **Final Primary Safety Endpoint:** For the final primary safety analysis, if a subject does not have full 12 months of follow-up and the subject has had a PAE at any time during the follow-up, the subject will be considered an event. If a subject does not have 12 months of follow-up but has at least 3 months of follow-up (similar to early success interim), this subject's last observed status will be carried forward for the 12-month safety endpoint as a proxy. If a subject without a PAE does not have at least 3 months of follow-up, this subject will be considered as missing the primary safety endpoint and will be excluded from the final primary safety analysis.
- **Final Primary Effectiveness Endpoint:** For the final effectiveness analysis, if a subject has an effectiveness failure at any time during the evaluation period, then the subject will be considered an event. Subjects without an effectiveness failure who (1) do not have full 12 months of follow-up and/or sufficient follow-up duration for the primary effectiveness endpoint (i.e., with at least 335 days of follow-up or arrhythmia monitoring post the index procedure), or (2) are missing all remote arrhythmia and holter monitoring records as required by protocol will be considered missing primary effectiveness endpoint and will be excluded from the final primary effectiveness analysis.

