### 8.1 Description of the Study Design

The design of the study will be carried out as an interventional, prospective, multicenter, single-arm clinical study. The study will enroll subjects with drug refractory, symptomatic PAF who are candidates for catheter ablation. All study subjects will be followed though 12 months post-ablation.

For the purpose of characterization of safety and to provide preliminary estimates for safety and acute effectiveness of the IRE system, Wave I of the study will enroll up to 40 subjects, who will undergo the index procedure and additional neurological, PV and esophageal assessments. For the purpose of safety and long-term effectiveness Wave II of the study will enroll up to 330 main study phase subjects plus roll-ins. Acute data from Wave I will be assessed for both, preliminary acute safety and acute performance, of the IRE system before proceeding with Wave II. Wave II enrollment can be initiated when all Wave I subjects have

reached 7 days follow up unless the Sponsor deems otherwise per sections 25 (Study Suspension or Termination) and 6.4.2 (Minimization of Risk).

An adaptive Bayesian design to will be used to determine the sample size. Two sample size selection interim analyses will be performed based on the primary effectiveness endpoint. Study success as defined by the main study endpoints will be analyzed for the respective Wave II analysis populations further described in the statistical section of this protocol (section 20). An additional interim analysis will be performed for claiming early trial success when 30 subjects reach full 12-month of follow-up and all subjects reach three months of follow-up.

In Wave II, the first 1-3 subjects for each ablating physician will be considered roll-in subjects to verify consistent workflow for study device components and to minimize any learning curve effects. Operators whom performed procedures in Wave I may be exempted from roll-ins for Wave II per training charter. The roll-in phase will include a maximum of 180 subjects.

Subjects will be evaluated prior to the procedure, prior to discharge, and post procedure at 7 days (Day 7-9), 1 month (Day 23-37), 3 months (Day 76-104), 6 months (Day 166-194), and 12 months (Day 335-379).

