#### 14.3 Post-Ablation Follow-up Schedule

The subject will be required to complete follow-up visits through 12 months post initial ablation procedure. Follow-up will be done at 7 days (phone call or clinic visit), 1, 3, 6 and 12 months (clinic visit).

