**At 1, 3, 6 and, 12-month follow-up visits, the following assessments will be performed:**

- Medical evaluation:
  - AEs
  - Cardiac and Anti-coagulation medication regimen
  - Cardiac related hospitalization and cardioversions
  - 12 Lead-ECG (if completed per standard of care)

- **Atrial arrhythmia monitoring as from month 3 (non-SOC)**
  - Remote Monitoring:  
Subjects will be provided with a remote monitoring device at the 3M FU visit and asked to record and transmit a minimum of 1 transmission ( $\geq 30$  seconds) every week through the end of the month 5 of FU. Starting at month 6 of FU, subjects will be asked to record and transmit a minimum of 1 transmission ( $\geq 30$  seconds) every month until the effectiveness evaluation period is completed (12 months post index procedure). Subjects will also be asked to transmit any symptom-triggered episode that occurs from the time they receive the remote monitoring device through the 12M FU visit. A core lab might be used to evaluate and assess the remote monitoring tracings.  
  
Remote monitoring will be conducted as follows:
    - Distribution and start by month 3
    - <6M: Weekly transmission of at least 1 scheduled recording
    - $\geq 6M$ : Monthly transmission of at least 1 scheduled recording
    - Conduct and transmit recording whenever symptoms are present
  - 24 Hour Holter:  
Holter monitor will be used at each follow-up visit to monitor the subjects' heart rhythm for 24 hours continuously. Following the 24h Holter, subjects will be contacted by the site to verify if symptoms are experienced during 24h Holter.
- Quality of life via the **Atrial Fibrillation Effect on Quality-of-Life (AFEQT™)** questionnaire (non-SOC), at Month 3, 6 and 12. Note: Patient questionnaires will only be used in countries with validated languages.
- **Cardiac CT/MRA**
  - **Wave I subjects:** is required to be performed at the 3M FU visit (non-SOC) or any other point in time when subject presents with symptoms of PV stenosis.
  - **Wave II subjects:** is only required to be performed if subject presents with symptoms of PV stenosis.
- **Wave I subjects only: Cerebral MRI, Neurological Exam and Neurological Evaluation using the MMSE, NIHSS and mRS (non-SOC)** are required to be performed if any neurological symptoms and/or cerebral ischemic lesions were identified at a prior evaluation. Note: Patient questionnaires will only be used in countries with validated languages.

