20.4.4.4 Handling of Missing Data

If a subject has not completed 12 months of follow-up but has had a PAE, then the subject will be considered an event for the final primary safety analysis. If a subject's follow-up time is less than 12 months and the subject has not had a PAE, then that subject will be excluded from the primary safety analysis.

For the early success interim analysis of the primary effectiveness endpoint, the subjects with incomplete follow-up data who are event free will be censored at the time of their last follow-up visit, and only their observed partial follow-up time will contribute to estimating model parameters.

For the final primary effectiveness analysis, if a subject has an effectiveness failure at any time during the evaluation period, then the subject will be considered an event. Subjects without an effectiveness failure who do not have full 12 months of follow-up will be excluded from the final primary effectiveness analysis.

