7.4.2.1 Early Success Interim Analysis of Primary Effectiveness Endpoint

At the time of the early success interim analysis, the primary effectiveness endpoint will be met if:

$$\Pr(p_E > 0.50 | x, n) > 0.9975$$

where p_E is the effectiveness success rate. If the posterior probability of the effectiveness success rate being greater than 50% is greater than 0.9975 then the study will be considered to have demonstrated effectiveness of the device at the early success interim analysis.

At the time of the early success interim analysis, the time-to-failure during the 9-month (39 weeks) post-blanking period will be modeled by using a piecewise exponential model. The model will consist of three distinct time intervals during the 9-month evaluation period: (0, 2], (2, 8], and (8, 39] weeks. Failure times during each time interval is assumed to be exponentially distributed with a different hazard rate in each segment. The model is:

$$f(t) = \exp(-th(t))$$

where

$$h(t) = \begin{cases} \lambda_1 & 0 < t \leq 2 \\ \lambda_2 & 2 < t \leq 8 \\ \lambda_3 & 8 < t \leq 39 \end{cases}$$

Vague Gamma prior distributions will be assumed for λ_1 , λ_2 , and λ_3 . Given hazard rates λ_1 , λ_2 , and λ_3 , the failure-free rate at 12 months (9 months post-blanking) p_E can then be estimated

by

$$p_E = \exp(-[2\lambda_1 + (8 - 2)\lambda_2 + (39 - 8)\lambda_3])$$

At the interim, the total number of primary effectiveness events and the total subject exposure time will be used to update the vague Gamma prior and obtain the posterior Gamma distribution for each segment. Then 10,000 random hazard rates will be sampled from the posterior distribution for each segment and each triplet set of hazard rates will be used to calculate p_E . The distribution of p_E is estimated based on the 10,000 calculated p_E s. If the probability of p_E being greater than 50% is greater than 0.9975 (99.75%), the trial will declare early success.

To investigate the robustness of the analysis result, the following sensitivity analyses will be performed in the mITT and PP analysis sets at the time of the early success interim analysis with the available data:

- **Sensitivity to Analysis Set**

The primary effectiveness endpoint will be analyzed in the mITT analysis set as a sensitivity analysis.

- **Kaplan-Meier Analysis**

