Kaplan-Meier estimates and plots will be used to characterize the time to first primary effectiveness event, including acute procedural failure and documented symptomatic/asymptomatic AF, AT or AFL recurrence following the initial ablation procedure. This will provide a non-parametric estimate of the primary effectiveness endpoint. The Kaplan-Meier analysis will account for all follow-up time for all subjects in the analysis set. Subjects with incomplete follow-up who remain failure free will be censored at the time of last observation. The probability of freedom from primary effectiveness failure at each monthly timepoint post blanking will be presented along with the one-sided 99.75% lower confidence bound using Greenwood's variance.

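### At the early-success look, event-free subjects stop adding exposure at their last visit while failures found after it still count, so a device at the planned 65% would rarely earn the early claim

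*SAP*

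**What the plan says.** For the early-success effectiveness analysis, Wave II SAP 7.4.3 states that "subjects with incomplete follow-up data will be censored at the time of their last follow-up visit (if event-free"). Protocol 20.4.4.4 agrees: "the subjects with incomplete follow-up data who are event free will be censored at the time of their last follow-up visit". For the two sample-size looks, the SAP bullet reads "subjects with incomplete follow-up data for the effectiveness endpoint will be censored at the time of their last follow-up visit". It has no event-free qualifier and adds that only observed partial follow-up contributes.

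At the early look the hazards come from events over exposure (SAP 7.4.2.1): "the total number of primary effectiveness events and the total subject exposure time will be used to update the vague Gamma prior".

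Protocol 14.3 schedules visits in the evaluation period at 3, 6 and 12 months only. Between them, subjects are "asked to record and transmit a minimum of 1 transmission" every week through month 5 and every month from month 6, and to send symptom-triggered recordings as well.

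Two other places use a different cut-off. The Kaplan-Meier analysis at the same look says "Subjects with incomplete follow-up who remain failure free will be censored at the time of last observation". Appendix I imputes from each patient's current observed time (10.3.1) and censors simulated dropouts at withdrawal (10.6.2).

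**The concern.** A hazard estimate needs events and exposure from the same stretch of time. At the early look they differ. A subject who is event-free at month 5 with weekly clean transmissions is cut back to the 3-month visit and adds almost no post-blanking exposure. A subject of the same age with AF on a week-2 transmission adds an event. Between months 6 and 12, event-free subjects stop at week 13 after blanking, while failures after week 13 are kept. Nearly everyone short of 12 months has incomplete follow-up at this look, so the rule touches most of the sample, not only dropouts.

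The early claim is at stake. Under the protocol summary, meeting the early-success criteria leads to CE Mark filing while 12-month follow-up continues. If the same mismatch operates at the sample-size looks, the decision to stop or continue enrolment is affected too.

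**Working it through.** **Inputs.** Hazards at a true rate of 65% (SAP Table 2): 0.1397, 0.0063 and 0.0037 per week over (0,2], (2,8] and (8,39] weeks after blanking. Dropout is 15% per year (10.6.2) and accrual is the realistic row of Table 1. The early threshold is 0.9975. The prior is Gamma(0.1, 0.1) in 10.3.1 and Gamma(1, 1) in 10.5; both were run for the early look. Visits fall at weeks 0, 13 and 39 after blanking.

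**Step 1: the plan's own figures.** The hazards give p_E = exp(-(2×0.1397 + 6×0.0063 + 31×0.0037)) = exp(-0.4319) = 0.65, as intended. The Appendix I design was then re-simulated with event-free subjects followed to their current observed time (2,500 trials, closest variant):

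| Quantity at 65% | Stated | Re-simulated |
|---|---|---|
| Early success | 0.8316 | 0.78 (0.77 to 0.86 across variants) |
| Futility stop | 0.0003 | 0.0000 |
| N = 180 / 255 / 330 | 0.5535 / 0.2854 / 0.1611 | 0.530 / 0.285 / 0.185 |
| Safety success | 0.8853 | 0.884 |
| Effectiveness success | 0.9457 | 0.972 |
| Overall power | 0.8395 | 0.862 |

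The match is close but not exact. Effectiveness success and power are 2 to 3 points high; the SAP leaves open how imputed dropouts enter the final test.

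**Step 2: the mismatch by hand, third interval.** Take subjects at risk at week 8 who are now at month 9 (week 26 after blanking).
- Probability of failure in weeks 8 to 26: 1 - exp(-18×0.0037) = 0.0644.
- True exposure per subject: 0.0644/0.0037 = 17.41 weeks. Of this, the failures' own time is 17.41 - 18×0.9356 = 0.57.
- Exposure under the visit rule: event-free subjects keep only weeks 8 to 13, so 5×0.9356 + 0.57 = 5.25 weeks.
- Hazard: 0.0644/5.25 = 0.0123, against 0.0037. Over 31 weeks this adds 0.38 to the cumulative hazard instead of 0.115.

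**Step 3: first interval.** Take subjects past week 2 but short of the 6-month visit.
- Probability of failure: 1 - exp(-2×0.1397) = 0.2438.
- True exposure: 0.2438/0.1397 = 1.745 weeks, of which the failures' own time is 1.745 - 2×0.7562 = 0.23.
- Under the visit rule only the 0.23 remains, so this group's hazard is 0.2438/0.23, about 1.06 per week, against 0.1397.

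Subjects beyond the relevant visit dilute both effects, so the overall bias depends on the follow-up mix.

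**Step 4: early-success look, simulated at 65%.** With the visit rule, median p_E is 0.55 and early success is 5.5% in the closest variant. It is 2.0% with dropouts excluded and the Gamma(1, 1) prior, 9.6% with visits spread over the protocol windows, and 20% with slow enrolment. A separate simulation of this look gave mean p_E of 0.53 to 0.57 and early success of 2 to 7%, against 63 to 94% with follow-up to the data cut. At a true rate of 70%, early success is 37%, against 0.8547 stated.

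**Step 5: sample-size looks, under each reading.** Expected data at N = 180, true rate 65%:

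| Rule | Events by interval | Exposure (weeks) | Hazards | Implied p_E |
|---|---|---|---|---|
| Both to current observed time | 20.0 / 1.7 / 1.3 | 143 / 279 / 342 | 0.1397 / 0.0062 / 0.0039 | exp(-0.4375) = 0.65 |
| Exposure to visit, all events kept | 19.9 / 1.8 / 1.2 | 74 / 161 / 125 | 0.269 / 0.011 / 0.0099 | exp(-0.9109) = 0.40 |
| Both cut at visit | 8.8 / 1.0 / 0.4 | 62 / 158 / 121 | 0.1415 / 0.0062 / 0.0035 | exp(-0.4287) = 0.65 |

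A hand check on the second row uses the shares in SAP section 6 (about 30% at 3 to 6 months and 20% beyond). That is 54 and 36 subjects. Events are 90×0.2438 = 21.9; exposure is 54×0.23 + 36×1.745 = 75 weeks; the hazard is 0.29.

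Futility stops at 65%: 0.0% with the first rule; 48% with the second (25% at 180, 23% at 255; 28% with visits spread over their windows, up to 75% across variants); 0.3% with the third. SAP Table 3.c states 0.03%.

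**The case against.** **The sample-size looks.** A reader might infer that an effective device would often be stopped for futility. The documents do not establish this. The sample-size bullet lacks the event-free qualifier, and read literally it cuts events and exposure at the same visit, which is unbiased. Keeping later failures follows only from combining that bullet with Appendix I 10.3.1, which counts observed events and imputes only patients without one. But 10.3.1 also works from current observed time, so it does not clearly support a visit cut for exposure alone. The futility figures are therefore conditional.

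**The consequence.** Crossing the futility bound stops enrolment; it does not fail the trial. About 87% of the 65%-effective trials stopped this way would still pass the final test at the reduced sample size, and simulated overall power is similar (0.88 against 0.86). Protocol section 25 lists futility only among circumstances that may warrant termination. The bias lowers p_E, so neither inflated type I error nor a broad loss of power should be inferred.

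**The size.** The runs date each failure at its exact time. Failures first found on a visit Holter carry the visit date and create no mismatch; that share was not varied. Fixing the 3-month visit at Day 90 is also severe, because the window runs to Day 104, which is week 2 after blanking. Spreading visits over the windows moderates the effect, but early success stays near 10%.

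**The wording.** One could read a transmission as a follow-up visit. The text points the other way: the safety bullet in SAP 7.4.3 uses the term for the scheduled 3-month visit, and the final-effectiveness bullet names follow-up and arrhythmia monitoring separately. If transmissions were meant, the bias largely disappears, but the plan has to say so.

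**Conclusion.** For the early-success look the rule is wrong as written: the qualifier is explicit in both documents, and 7.4.2.1 counts all events. At a true rate of 65%, mean p_E is about 0.53 to 0.57 and early success roughly 2 to 20%, against 83% stated. This assumes that a follow-up visit means the scheduled 3-, 6- or 12-month visit, that failures are dated when they occur between visits, and the Appendix I hazards, accrual and dropout.

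For the sample-size looks the finding is conditional: about 28 to 75% false futility stops if later failures are kept, about 0.3% if events and exposure share the visit cut.

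The harm is a lost early claim and possibly wrong enrolment decisions. Because Appendix I describes observed or withdrawal time, its stated operating characteristics do not describe the visit rule. The approximate match in Step 1 is consistent with follow-up to the data cut but does not prove that this is what was simulated.

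**What to change.** In both the sample-size and early-success effectiveness bullets of SAP 7.4.3, and in protocol 20.4.4.4:
- censor event-free subjects at their last evaluable rhythm recording, remote or Holter, up to one data cut-off date;
- count only failures dated on or before that cut-off;
- use the same rule for the Kaplan-Meier analysis;
- confirm that the Appendix I simulations used this rule, and re-run them if they did not.

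Cutting both events and exposure at the last visit would also remove the bias, but it discards monitored time: early success at 65% is then 59%, against 78% with follow-up to the current observed time.

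The cost is wording in two documents, one data derivation and a check of existing simulation code. No new data are needed.

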#### 20.4.4 Primary Endpoint Analyses and Associated Hypotheses

The primary safety endpoint will be summarized descriptively in the mITT-Wave I analysis set after all Wave I subjects complete the 12-month follow-up. Similarly, the primary effectiveness endpoint will be summarized descriptively in the PP-Wave I analysis set after all Wave I subjects complete the 12-month follow-up.

For the main study phase, the PAE rate will be formally compared against a performance goal of 14%. Additionally, the primary effectiveness success rate will be compared to a performance goal of 50% for the main study phase. The primary safety endpoint analysis for the main phase will be performed in the mITT-Wave II analysis set and the primary effectiveness analysis will be performed in the PP-Wave II analysis set.

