10.2 Sample Size Justification

The methods described in Broglio et al.¹ will be used to determine the sample size based on the effectiveness endpoint. Sample size selection interim analyses will be performed when 180 and 255 patients are enrolled in the mITT analysis set. Predictive probabilities for trial success will be used to determine whether the sample size at the time of the interim analysis will be sufficient or

if the trial will continue to the full sample of 330. The power for testing the primary safety endpoint is greater than 80% at all sample sizes greater than or equal to 180 subjects, assuming a primary safety rate of 7% with a performance goal of 14%.

It is assumed that there is a 5% dropout rate for the safety endpoint and a 15% dropout rate for the effectiveness endpoint. The sample size will provide greater than 80% power at one-sided significance level of 2.5% for each endpoint assuming that a true safety rate of 7% and a true effectiveness rate of 65% compared to the performance goals of 14% and 50% respectively.

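### The missing-data rules let sparse rhythm monitoring count as event-free at the final and interim analyses, which can only raise the effectiveness estimate, and set no compliance threshold

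*SAP*

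**What the plan says.** The primary effectiveness endpoint is freedom from arrhythmia documented on recordings between Day 91 and Day 365 (SAP Wave II 7.4.2). Protocol 14.3 schedules weekly remote transmissions from month 3 to the end of month 5, monthly ones from month 6, and 24-hour Holters at the 3-, 6- and 12-month visits. The 12-lead ECG is collected only where it is standard of care.

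**Final analysis.** Under SAP (Wave II) 7.4.3, an event-free subject is missing in either of two cases. The first is a follow-up duration below the requirement, which is met "with at least 335 days of follow-up or arrhythmia monitoring post the index procedure". The second is a complete absence of recordings: such subjects "are missing all remote arrhythmia and holter monitoring records as required by protocol will be considered missing primary effectiveness endpoint". SAP (Wave I) 7.4.3 has the same rule.

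**Interims.** The same section states for the early-success analysis that "subjects with incomplete follow-up data will be censored at the time of their last follow-up visit (if event-free"). The sample-size interims also censor at the last visit. Subjects who refuse the monitoring device are excluded, but only from the early-success analysis.

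**Decision rules.** Protocol 20.4.4 says that "the primary effectiveness success rate will be compared to a performance goal of 50% for the main study phase". The final criterion in SAP 7.4.2.2 is "If the posterior probability of the effectiveness rate being greater than 50% is greater than 0.9775". The early criterion in SAP 7.4.2.1 is "If the probability of p_E being greater than 50% is greater than 0.9975 (99.75%), the trial will declare early success".

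**The concern.** The endpoint is defined by recordings, but evaluability hardly depends on them. Because the duration test accepts follow-up or monitoring, a clinic contact at or after Day 335 satisfies it, and one record satisfies the other test. That record could be a 3-month Holter taken between Day 76 and Day 90, before the evaluation period opens, because the 3-month visit window is Day 76 to 104. Such a subject enters the beta-binomial count as a success.

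At the interims, time between the last recording and the last visit is counted as observed and event-free. A subject who accepts the device but never transmits still contributes exposure.

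The error runs one way: a missed recurrence turns a failure into a success or adds event-free time. With a single arm and a fixed 50% goal, no comparator shares the bias. The best-case, worst-case and tipping-point analyses act only on outcomes classed as missing, and these outcomes are not. Early success can also lead to CE-mark filing while follow-up continues (Protocol summary, Statistical Analysis).

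**Working it through.** **Inputs from the documents.** Goal 50%; Beta(1,1) prior; final cutoff 0.9775 (SAP 7.4.2.2). Sample sizes 180, 255 and 330. On dropout, SAP 10.2 says "It is assumed that there is a 5% dropout rate for the safety endpoint and a 15% dropout rate for the effectiveness endpoint". Evaluable numbers are therefore 180 × 0.85 = 153, 255 × 0.85 ≈ 217 and 330 × 0.85 ≈ 280.

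**Reproducing the plan's figure.** SAP 10.2 says "The sample size will provide greater than 80% power at one-sided significance level of 2.5% for each endpoint". The exact binomial under the final rule gives:

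| n | successes needed | P(success) at 50% | P(success) at 65% |
|---|---|---|---|
| 153 | 89 | 0.026 | 0.967 |
| 217 | 124 | 0.021 | 0.993 |
| 280 | 157 | 0.024 | 0.999 |

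Power above 80% for effectiveness reproduces.

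**Effect of missed recurrences.** Let p be the true rate, f the share of evaluable subjects who are poorly monitored, and m the share of their true failures that is never recorded. Then

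expected observed rate = p + (1 − p) × f × m.

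The documents give neither f nor m, so both are assumptions.

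**What the SAP's hazards say about m.** At a 50% failure-free rate, Table 2 in SAP Appendix I (10.6.1) gives 0.2248, 0.0101 and 0.0059 per week.
- Event-free at week 2: exp(−2 × 0.2248) = 0.638. Share of all failures by then: (1 − 0.638)/0.50 = 72%.
- Event-free at week 8: exp(−0.4496 − 6 × 0.0101) = 0.600. Share by then: (1 − 0.600)/0.50 = 80%.

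A subject monitored fully for the first 2 or 8 post-blanking weeks who then lapses can hide at most about 28% or 20% of failures. A subject with a single recording could hide more.

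**Chance that a true 50% device passes the final rule:**

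| m | f | expected rate | n = 153 | n = 280 |
|---|---|---|---|---|
| 0 | any | 50% | 2.6% | 2.4% |
| 0.20 | 5% | 50.5% | 3.4% | 3.5% |
| 0.28 | 5% | 50.7% | 3.8% | 4.1% |
| 0.20 | 10% | 51.0% | 4.5% | 5.1% |
| 0.28 | 10% | 51.4% | 5.5% | 6.6% |
| 0.50 | 5% | 51.25% | 5.1% | 6.0% |
| 0.50 | 10% | 52.5% | 9.3% | 12.8% |
| 1.00 | 5% | 52.5% | 9.3% | 12.8% |
| 1.00 | 10% | 55.0% | 24.0% | 38.3% |

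A larger sample does not cure the bias.

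**Whole design, indicative only.** A simulation of the adaptive design at a true 50%, with Gamma(0.1, 0.1) priors and realistic enrollment, gave overall success in 3.8-11.5% of runs at f = 10%, m = 0.50, against 0.5-2.3% with full detection. Each range covers two readings of how dropouts are handled. The early-success criterion alone was met in about 2% of runs, against 0.25-0.35%. The simulation does not match the SAP's 94.57% for winning on effectiveness (Table 3.a) or its 1.68% type I error (Table 3.b). The SAP does not fully specify its simulation, so this does not show those figures to be wrong.

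**The case against.** **The Per Protocol set is a safeguard.** It is the primary effectiveness set, and SAP (Wave II) 5.1 excludes major deviations through an open-ended list. Protocol 17 counts a missed test as a deviation, and the sponsor tracks missing data (Protocol 24.1.3). SAP 7.4.3 also allows case-by-case handling. A subject with one early recording and a late visit is an obvious candidate for exclusion. This stands in part: a reader might infer that non-compliance always becomes success, and the documents do not support that. But no passage names monitoring compliance as a major deviation or sets a threshold, so removal is discretionary in an open-label single-arm trial.

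**The bias may be small.** Subjects with no recordings are already excluded at the final analysis, most failures are expected early, and symptom-triggered transmissions will catch some. This also stands. A reader might take the 9.3% and 24% at m = 1 as the expected effect, but those figures require that no failure is ever detected in the poorly monitored group. Against that, the endpoint includes asymptomatic episodes, which symptom-triggered recording does not target.

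**Exposure does not enter the final result.** Correct: it matters only in the interim piecewise model. The final analysis is a binary count, affected through the evaluability rule alone.

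**Kaplan-Meier might reveal the problem.** SAP 7.4.2.1 and 7.4.2.2 censor failure-free subjects with incomplete follow-up at a last-observation date. It is undefined and could mean the last recording, so one cannot say that no planned analysis would show the effect. Nor can one rely on it as written.

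**Conclusion.** The point holds as a gap in prespecification with a known direction and an unknown size. Followed as written, the rules credit unmonitored time as event-free. At a true 50% and n = 153, the false-success chance under the final rule moves from 2.6% to 3.4-3.8% (5% of subjects lapse after early monitoring) or 4.5-5.5% (10% lapse). It reaches 5.1% or 9.3% if half of their failures are missed. The figures of 9.3% and 24% are the upper extreme of no detection, and the rise is zero if no recurrence is missed.

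These figures rest on assumed values of f and m, on 15% being non-evaluable, and on no discretionary exclusion from the Per Protocol set. They do not show that the trial's actual rate is inflated or that the SAP's type I error simulations are wrong. They show that the 2.5% control claimed in SAP 4 depends on near-complete detection, which the evaluability rule does not secure.

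**What to change.** 1. In SAP (Wave II) 7.4.3, for both kinds of interim, and in the Kaplan-Meier analyses of 7.4.2.1 and 7.4.2.2, censor event-free subjects at the last valid rhythm recording on or after Day 91. Give no event-free exposure to a subject with no such recording.
2. Prespecify a sensitivity analysis of the final primary endpoint limited to subjects who meet a stated minimum monitoring compliance, spread over Day 91-365. Calculate compliance on recordings due up to failure or end of follow-up, apply it regardless of outcome, and show the result beside the current rule.
3. Extend the worst-case and tipping-point analyses to event-free subjects below that minimum.
4. Make the matching change to the rule in SAP (Wave I) 7.4.3.

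Merely requiring a recording on or after Day 335 would not do, because a lone late recording would still qualify. Dropping only event-free poor compliers while keeping their detected failures over-corrects. At a true 50%, f = 10% and m = 0.50, the expected rate becomes 0.45/(0.45 + 0.45 + 0.025) = 48.6%.

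The cost is SAP wording, a little more analysis and slightly less event-free exposure at the interims.
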